7 DESCRIPTION OF STUDY ASSESSMENTS AND PROCEDURES

Before performing any study procedures, all potential participants will sign an ICF. Participants will have the opportunity to have any questions answered before signing the ICF. The Investigator must address all questions raised by the participant.

The study assessments to be performed at each visit and timepoint are specified in the study [Schedule of Procedures – Part 1](#) and [Schedule of Procedures – Part 2](#).

7.1 Efficacy Assessments

7.1.1 eGFR Determination

The eGFR values for the primary analysis will be calculated according to the 2021 CKD-EPI formula (CKD-EPI_{Cr_R}) (Appendix 1 ([Section 13.1](#))) from the serum creatinine concentrations taken during the Screening Period and at the visits specified in the [Schedule of Procedures – Part 1](#) and [Schedule of Procedures – Part 2](#) of the study. During the Screening Period, serum creatinine assessments obtained at Visits 1a, 2, and 3 or Visits 1b, 2, and 3 (if Visit 1b is required) will be used to determine the mean eGFR for analysis purposes. The averaged value will be used as the eGFR baseline. For Part 2, the serum creatinine assessments obtained during Follow-up Period I (Visit 23, Visit 24, and Visit 25) will be used as the eGFR baseline. Every attempt will be made to draw blood samples for eGFR determination at approximately the same clock time during Visits 1a/1b, 2, and 3 and Visits 23, 24, and 25, and again at Visits 43, 44, and 45 for a given participant.

As an exploratory endpoint, eGFR will also be assessed by the measurement of serum creatinine and serum cystatin C using a novel CKD-EPI equation (CKD-EPI_{Cr-cys_R}) (Appendix 1 ([Section 13.1](#))). Along with serum creatinine concentrations, serum cystatin C will be obtained at Visits 1a, 2 and 3 or Visits 1b, 2 and 3 and during Follow-up Period I (Visits 23, 24, and 25) and during Follow-up Period II (Visits 43, 44 and 45). The mean of the 3 eGFR measurements calculated from the CKD-EPI_{Cr-cys} equation during each period will be used for the baseline and follow-up period for analyses of the exploratory eGFR endpoint. To reduce potential decision errors, eGFR calculated from the CKD-EPI_{Cr-cys_R} equation will not be shared with sites as all eligibility and treatment decisions will be based on eGFR calculated from the CKD-EPI_{Cr_R} equation.

Alteration in the metabolism of creatinine based on changes in meat intake and exercise may impact accuracy of serum creatinine and determination of eGFR. Measures to reduce variability are provided in [Section 5.6](#).

7.1.2 MRI Assessment

MRI scans will be obtained for 2 purposes:

- 1) to qualify each participant's participation during Screening based on the Mayo Clinic ADPKD Image Classification (prognostic criteria) ([Irazabal et al, 2015](#));
- 2) to investigate lixivaptan's pharmacodynamic effect on TKV and LV.

Participants will undergo a standardized abdominal MRI assessment without use of intravenous contrast agent for the determination of TKV (combined kidney volume of both kidneys) and LV at 3 timepoints: Screening; Follow-up Period I (Visit 25); and Follow-up Period II (Visit 45).

The MRI acquisition protocol will be detailed in the study imaging manual. MRI images will be sent to a blinded central imaging vendor for a) quality control; b) determination of Mayo Clinic ADPKD Image Classification (Class 1 [typical] or Class 2 [atypical] at Screening only); and c) measurement of TKV and LV.

Participants with ferro-magnetic prostheses, aneurysm clips, severe claustrophobia, or other contraindications or exclusions interfering with MRI measurements will not be enrolled in the study. Investigator should seek MRI safety guidance from the local MRI facility.

To maintain study blinding, volumetric calculations and other derived data from MRI imaging obtained after randomization (Visit 9) will not be shared with the participant, the investigator, the clinical sites, the sponsor, or the CRO.

7.1.3 Urine Osmolality

Fasting (≥ 8 hrs, except for water) spot first AM urine collections will be obtained at the timepoints specified in the [Schedule of Procedures – Part 1](#) and [Schedule of Procedures – Part 2](#) of the study. Participants will be provided a urine collection container in advance of each visit where U_{osm} is determined. They will be asked to completely empty their bladders upon arising in the morning and then provide a spot urine specimen within the next 30-45 minutes, prior to taking the morning dose of study drug. They will bring that specimen to their clinic visit. All U_{osm} assessments in the study will be conducted using this method.

All samples will be sent to the central laboratory for analysis. To maintain study blinding, results of U_{osm} assessments obtained after randomization (Visit 9) will not be shared with the participant, the investigator, the clinical sites, the sponsor, or the CRO.

7.2 Health Outcomes Assessments

7.2.1 Medical Resource Utilization

Medical resource utilization will be evaluated throughout Part 1 and Part 2 of the study. Beginning at Visit 3, participants reporting clinical events as either AEs or SAEs should be questioned on whether any of the clinical events resulted in medication use or medication changes (e.g., change in dose; change in medication); an unplanned office visit, an urgent care visit and/or an emergency department visit or in-patient hospitalization in order to diagnose, treat or manage the clinical event). Data collected will be entered in the appropriate eCRF.

7.2.2 ADPKD- Impact Scale

The ADPKD-IS ([Oberdhan et al, 2017](#)), a participant self-administered questionnaire consisting of 14 items, measures the impact of ADPKD on a patient's health-related quality of life (HRQoL) using 3 conceptual domains: physical, emotional, and fatigue plus 4 additional questions. Each item is measured on a scale of 1 (not difficult/bothered at all) to 5 (extremely difficult/bothered) with a recall period of 14 days. Each domain is scored by summing the scores of all items in the domain and dividing the total number by the number of items in that domain. Each domain score is measured on a scale of 1–5, from 1, not difficult/bothered at all, to 5, extremely difficult/bothered, with a recall period of 14 days. The ADPKD-IS will be administered throughout Part 1 and Part 2 of the study at the time-points specified in the [Schedule of Procedures – Part 1](#) and [Schedule of Procedures – Part 2](#). In this study, participants will directly record their responses into an electronic data capture device (i.e., tablet). During remote visits, participants will record their responses on a paper copy, which will later be transcribed into the database by site personnel.

7.2.3 ADPKD- Pain and Discomfort Scale

ADPKD-PDS ([Oberdhan et al, 2015](#)), a participant self-administered questionnaire consisting of 20 items, measures the impact of three distinct types of ADPKD-related pain: dull kidney pain, sharp kidney pain, and fullness/discomfort. Each item is measured on a 5-point scale from 1 (no pain/discomfort) to 5 (extreme pain/discomfort). The questionnaire has a recall period of 7 days. The ADPKD-PDS will be administered throughout Part 1 and Part 2 of the study at the time-points specified in the [Schedule of Procedures – Part 1](#) and [Schedule of Procedures – Part 2](#). In this study, participants will directly record their responses into an electronic data capture device (i.e., tablet). During remote visits, participants will record their responses on a paper copy, which will later be transcribed into the database by site personnel.

7.2.4 ADPKD- Urinary Impact Scale

The ADPKD-UIS ([Oberdhan et al, 2013](#)), a participant self-administered questionnaire, measures the burden of urinary concerns in ADPKD using 11 items that assess 3 domains: daytime urinary frequency, daytime urinary urgency, and nocturia. Each item is measured on a scale from 1 (not difficult/bothered) to 5 (very difficult/bothered). ADPKD-UIS measures each domain by summing the scores for all items in the domain and dividing it by the number of items in that domain. The questionnaire has a recall period of 7 days. The ADPKD-UIS will be administered throughout Part 1 and Part 2 of the study at the time-points specified in the [Schedule of Procedures – Part 1](#) and [Schedule of Procedures – Part 2](#). In this study, participants will directly record their responses into an electronic data capture device (i.e., tablet). During remote visits, participants will record their responses on a paper copy, which will later be transcribed into the database by site personnel.

7.3 Safety and Tolerability Assessments

The safety and tolerability of lixivaptan will be assessed by evaluation of AEs, SAEs, physical examinations, vital sign measurements, ECGs, and clinical laboratory parameters (hematology, clinical chemistry including liver chemistry tests, and urinalysis). Additional safety assessments may be performed as needed at the discretion of the Investigator. Safety assessments will be performed throughout the study as described in the [Schedule of Procedures – Part 1](#) and [Schedule of Procedures – Part 2](#). Assessment windows are presented in [Table 3](#) and [Table 4](#).

7.3.1 Body Height, Weight, and BMI

Body height (inches or centimeters) and weight (pounds or kilograms) will be measured at Screening Visit 1a to the nearest tenth, and BMI will be calculated automatically by the eCRF functionality ($\text{BMI} [\text{kg}/\text{m}^2] = \text{body weight} [\text{kg}] / \text{height}^2 [\text{m}^2]$). Body weight will be subsequently measured as described in the [Schedule of Procedures – Part 1](#) and [Schedule of Procedures – Part 2](#). It is preferable to use the same scale at each visit where body weight is measured, and measurements of height and weight will be without the participant wearing shoes.

7.3.2 Physical Examinations and Medical History

A complete physical examination will be performed during Screening Visit 1a. Brief physical examinations will subsequently be performed at the timepoints specified in the study [Schedule of Procedures – Part 1](#) and [Schedule of Procedures – Part 2](#).

A complete physical examination will include, at a minimum, height and weight, general appearance, and assessment of the following systems: skin, head, ears, eyes, and throat, respiratory system, cardiovascular system, gastrointestinal system, neurologic system, blood and lymphatic systems, and the musculoskeletal system. The physical examination may be performed by the Investigator, a sub-investigator who is a medical doctor, a qualified nurse practitioner or a physician's assistant in accordance with the site's current practice and local requirements, as applicable.

Brief physical examinations include, at a minimum, weight, and assessment of the following systems: chest and heart auscultation, abdominal examination, neurologic condition (i.e., alert and oriented x3; not including cranial nerves), and edema and hydration assessment. The brief physical examination may be performed by the same individuals who can perform a complete physical examination.

Physical examination findings noted during Screening Visit 1a will become part of medical history. New physical examination findings observed after initiation of study drug will be classified as being in 1 of 3 categories: normal, abnormal but not clinically significant (NCS), or abnormal and clinically significant (CS). All CS findings will be reported as AEs.

Physical examinations may be performed at various unscheduled time points if deemed necessary by the Investigator. Symptom-directed physical examinations will be performed as appropriate for participants experiencing AEs.

Medical history, smoking and alcohol history, and demographic data will be recorded at Visit 1a as specified in the [Schedule of Procedures – Part 1](#).

7.3.3 Vital Sign Measurements

Vital sign measurements will include systolic blood pressure, diastolic blood pressure, and pulse rate and will be performed at the timepoints specified in the [Schedule of Procedures – Part 1](#) and [Schedule of Procedures – Part 2](#). Respiratory rate and body temperature will be measured once at Screening Visit 1a.

Participants will remain at rest in a seated position for a minimum of 5 minutes before vital sign measurements are obtained. For all participants, blood pressure and pulse rate will be measured once at each specified time using an automated sphygmomanometer. Blood pressure measurements will be taken with the appropriate cuff size and in the same arm (whenever possible) for the duration of the study. The arm should be positioned level with the heart and the blood pressure cuff applied directly to the skin (not over clothing). A confirmatory repeat vital sign measurement may be performed at the discretion of the Investigator. Although sitting is the standard position for measurement of vital signs, a site that uses a different standard of care, e.g., semi-recumbent, may utilize that position as long as all measurements at that site are done in the same position. Other positions to obtain vital signs may be used after discussion with the medical monitor. Any confirmed, clinically significant vital sign measurements should be recorded as medical history at Screening Visit 1a and as an AE thereafter. If other procedures are scheduled at the same timepoint, vital signs should be obtained first, before an ECG and/or blood draw.

7.3.4 12-Lead ECGs

Standard 12-lead ECGs will be performed at the timepoints specified in the study [Schedule of Procedures – Part 1](#) and [Schedule of Procedures – Part 2](#).

ECG intervals will be measured using an ECG machine that automatically calculates the HR and measures PR, QRS, QT and QTcF. The same ECG machine should be used for the same participant throughout the study.

ECGs will be obtained with the participant remaining in a supine or semi-recumbent position following 5 minutes of rest. All ECGs throughout the study for a given participant should be measured in the same position, i.e., either all in a supine position or all in a semi-recumbent position. If other procedures are scheduled at the same timepoint, the ECG should be obtained after vital sign measurements and/or before the scheduled blood draw.

ECGs will be transmitted electronically to the central ECG laboratory for analysis according to the instructions provided by the laboratory to be read by a cardiologist. The ECGs will be classified as being in one of three categories: normal, abnormal but not clinically significant (NCS), or abnormal and CS. All CS findings should be reported as medical history at Screening Visit 1a and as AEs thereafter.

Additional ECGs may be performed if deemed medically appropriate.

7.3.5 Clinical Laboratory Tests

Blood and urine specimens will be collected for clinical laboratory determinations (hematology, clinical chemistry including serum sodium, liver chemistry and serum creatinine and serum cystatin C, serology, and urinalysis) by the central laboratory and local urine pregnancy tests (WOCBP only) at the timepoints specified in the study [Schedule of Procedures – Part 1](#) and [Schedule of Procedures – Part 2](#). A confirmatory assessment through the central laboratory should be obtained as soon as possible for any CS abnormal laboratory parameter if deemed necessary by the Investigator. All CS findings should be reported as medical history at Screening Visit 1a and as AEs thereafter. Repeat testing for abnormal liver chemistry tests is described in [Section 7.3.7.1](#). Any other repeat laboratory testing for values that are not CS should first be discussed with the medical monitor before such tests are ordered. All positive urine pregnancy testing results will be confirmed by a serum pregnancy test at the central laboratory.

With the exception of participants' at-home collection of urine specimen for measurement of urine osmolality by the central laboratory, laboratory tests required by the protocol do not require overnight fasting. Mild elevations in serum creatinine or serum sodium are known pharmacodynamic effects of vasopressin antagonists like lixivaptan, therefore, confirmatory assessments for serum creatinine and serum sodium will be at the Investigator's discretion.

Clinical laboratory parameters for analysis are presented in [Table 8](#).

Table 8. Clinical Laboratory Parameters

Chemistry	Hematology	Urinalysis
Albumin	Hematocrit	pH
Blood urea nitrogen (urea)	Hemoglobin	Specific gravity
Calcium	Red blood cell count	Protein
Chloride	Quantitative platelet count	Glucose
Carbon dioxide (CO ₂)	White blood cell (WBC) count with differential (total and %)	Ketones
Glucose	only if WBC count is abnormal:	Bilirubin
Phosphorous	Neutrophils	Blood
Potassium	Lymphocytes	Urobilinogen
Protein	Monocytes	Leukocytes
Sodium*	Eosinophils	Nitrite
Uric Acid	Basophils	Microscopic examination (if positive for blood, protein, nitrite, or leukocytes)
Serum Creatinine		
Creatinine, enzymatic		
Serum cystatin C		
Serology (Screening)	Liver Chemistry	Other Tests
Hepatitis B surface antigen	Alkaline phosphatase	Urine osmolality
Hepatitis C antibody (reflex HCV RNA for all Hepatitis C antibody positive or reactive results)	ALT AST Bilirubin (Total and Direct)	Urine or serum pregnancy test

*Serum sodium will be assessed at all time-points specified in the Schedule of Procedures either as part of chemistry or liver chemistry testing.

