3.7. Sample Size

Part 1:

Based on the results of the REPRISE trial with tolvaptan (Torres et al, 2017), it is assumed that the standard deviation for the primary efficacy endpoint, change from baseline to post-treatment follow-up in mean eGFR, is 6.20 mL per minute per 1.73 m². Assuming a between-treatment group difference of -1.40 mL per minute per 1.73 m² and a randomization ratio of 2:1 for lixivaptan to placebo, a sample size estimate of 1314 participants (438 placebo-treated participants and 876 lixivaptan-treated participants) is required to achieve 90% power at a significance level of 0.01. This estimate has been adjusted up to 1350 participants (450 placebo participants and 900 lixivaptan participants). It is estimated that approximately 2250 participants will need to be screened in order to randomize 1350 participants.

Part 2:

This is a convenience sample based on the number of participants who elect to continue into Part 2. It is estimated that approximately 1350 participants will be randomized in Part 1. All participants except those who discontinue due to an adverse event or withdraw consent will continue into Part 2. Approximately 90% (1215) of Part 1 participants are anticipated to continue into Part 2.

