9.3. Clinical Laboratory Evaluations

For Part 1, descriptive statistics (n, mean, standard deviation [SD], median, minimum, and maximum) for clinical laboratory data and changes from baseline at each post-baseline time point will be presented by treatment group (treatment cohort for Part 2).

The baseline value is the last value observed prior to first administration of study drug and any information obtained after first administration of study drug is regarded as post-baseline information. The change-from-baseline variables will be calculated as the post-baseline value minus the value at baseline. Change from baseline on continuous data will be summarized using descriptive statistics at each post-baseline time point by treatment group. For categorical data, change from baseline will be summarized using frequency and proportion at each post-baseline timepoint by treatment group (treatment cohort for Part 2).

For all continuous clinical laboratory variables, a shift table comparing the baseline value (normal, low, and high) to the last observation on treatment will be presented by treatment group (treatment cohort for Part 2).

For urinalysis, a shift table (using number of participants with results of negative, trace, or positive) comparing the baseline value to the maximum value will be presented by treatment group (treatment cohort for Part 2).

For Part 2, descriptive statistics (n, mean, standard deviation [SD], median, minimum, and maximum) for clinical laboratory data and changes from baseline (last value observed during Follow-up Period I in Part 1) at each post-baseline time point will be presented for all participants for each scheduled time point.

For all continuous clinical laboratory variables in Part 2, a shift table comparing the baseline (last value observed during Follow-up Period I in Part 1) value (normal, low, and high) to the last observation on treatment will be presented for all participants.

For urinalysis in Part 2, a shift table comparing the baseline (last value observed during Followup Period I in Part 1) value to the maximum value will be presented for all participants (using number of participants with results of negative, trace, or positive).

Potentially clinically significant results of clinical laboratory evaluations identified using prospectively defined criteria (Table 3) will also be summarized descriptively by treatment group (treatment cohort for Part 2).

Lab Test Category	PCS Criteria
	Sodium: <132 mmol/L

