	Sodium: >149 mmol/L
	Potassium:<2.5 mmol/L
	Potassium: >6.5 mmol/L
	Calcium: <1.62 mmol/L
Chemistry	Calcium:>3.49 mmol/L
	Uric acid:>715 µmol/L
	Albumin: <25 g/L
	eGFR: Decrease from baseline of ≥25%
	Glucose: ≤2.5 mmol/L
	Glucose:≥14.0 mmol/L
	Leukocytes: $\leq 2.5 \times 109/L$
	Leukocytes: $\geq 15.0 \ge 109/L$
	Neutrophils: $\leq 1.5 \ge 109/L$
Hematology	Platelets: $\leq 50.0 \text{ x } 109/\text{L}$
	Hemoglobin: Decrease from baseline of ≥ 20 g/L or ≤ 80 g/L (absolute value)
	Hematocrit: Decrease from baseline of \geq 10% (absolute change) or \leq 24% (absolute value)
Urinalysis	Glucose: ≥2+
	RBC/HPF: >10
	Protein: >2+
	Ketones: > 2 +
	Leukocytes: >10

Table 3: Potentially Clinically Important Criteria (PCS): Laboratory

For Part 1 and Part 2, individual data listings of clinical laboratory results will be presented for each participant. Values that meet laboratory PCS will be flagged in the clinical laboratory listings (see Table 3).

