11.2. Hepatic Events Review Committee (HERC)

In order to adequately characterize the liver safety profile of lixivaptan, additional testing and data collection will be required for any participant who develops clinically significant liver chemistry test abnormalities and/or signs or symptoms of liver dysfunction during the study. The HERC will independently and in a treatment-blinded manner expertly judge attribution to study drug as detailed in the HERC Charter and will communicate in writing with the sponsor and the IDMC. The IDMC reviews data at a study-level and, as such, its recommendations will not be made known to the HERC so as not to bias the HERC when adjudicating participant cases. These two committees are independent and will have a one-way line of communication from HERC to IDMC. The results of the HERC review and adjudication will be incorporated into the reporting of the safety results of the trial.

12. Statistical Analysis and Reporting

Data processing, tabulation of descriptive statistics, calculation of inferential statistics, and graphical representations will primarily use SAS (release 9.4 or higher). If the use of other software is warranted, the final statistical methodology report will detail what software, including version, was used for what purposes.

Continuous (quantitative) variable summaries will include the number of participants (n) with non-missing values, mean (geometric mean for log-transformed data), standard deviation (SD), median, minimum, and maximum.

Categorical (qualitative) variable summaries will include the frequency and percentage of participants who are in the particular category or each possible value. In general, the denominator for the percentage calculation will be based upon the total number of participants

with non-missing data in the study population for the treatment groups, unless otherwise specified.

The minimum and maximum will be reported with the same degree of precision (i.e., the same number of decimal places) as the observed data. Measures of location (mean and median) will be reported to 1 degree of precision more than the observed data and measures of spread (SD) will be reported to 2 degrees of precision more than the observed data.

Percentages will be presented to 1 decimal place, unless otherwise specified.

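### Neutrophils and urine microscopy are reflex tests, but the SAP's default denominator would report their abnormality percentages among reflex-tested participants only

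*Protocol*

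**What the plan says.** Protocol Section 7.3.5, Table 8, heads the five differential cell types, neutrophils first, with the condition "only if WBC count is abnormal". In the urinalysis column it lists "Microscopic examination (if positive for blood, protein, nitrite, or leukocytes"). Both are reflex tests: the sample's total white count or dipstick decides whether they are done.

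SAP Section 9.3 then states: "Potentially clinically significant results of clinical laboratory evaluations identified using prospectively defined criteria (Table 3) will also be summarized descriptively by treatment group". Table 3 in that section includes neutrophils at or below 1.5 x 10^9/L, urine red cells above 10 per high-power field, and a urinalysis row reading "Leukocytes: >10" with no unit. Section 9.3 also asks for descriptive change-from-baseline summaries, and for baseline-to-last-value shift tables for all continuous laboratory variables. It names no denominator for the PCS summaries and does not say how an untriggered test is to be counted.

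SAP Section 12 supplies the general rule: the percentage denominator is the number of participants "with non-missing data in the study population for the treatment groups, unless otherwise specified".

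**The concern.** A participant whose trigger test was normal has no neutrophil or microscopy result. Under the Section 12 rule that participant leaves the denominator, although a blood count or dipstick was done and was unremarkable. The table would look like an incidence by arm but would show the proportion abnormal among those selected for further testing.

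Two things are at stake. First, the level: the percentage rises as the share tested falls. Second, the comparison: two arms with the same share of affected participants show different percentages if their trigger rates differ. Haematuria is named as a feature of the disease in Protocol Section 1.2, so the urine red-cell row is one that a reader would look at.

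Neutrophils have a further problem. A count at or below 1.5 with a normal total white count is not captured by protocol-scheduled testing, so no choice of denominator gives a true incidence. A baseline neutrophil value also exists only where the baseline white count was abnormal, so the differential shift and change tables would cover few participants.

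**Working it through.** The documents state no rate for these abnormalities and no trigger rate, so there is no plan figure to reproduce. What follows shows the mechanism on assumed rates.

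**Inputs**
- Planned arm sizes, from SAP Section 3.7: 900 lixivaptan and 450 placebo. They are used for illustration only.
- t, the share of an arm reflex-tested at least once: assumed 5% to 50%.
- c, the share of an arm with a PCS value found on reflex testing: assumed 0.5% to 2%.

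**Step 1. Effect on the level.** Over non-missing data the printed percentage is c/t. Over everyone sampled it is c. The ratio is 1/t. For the lixivaptan arm with c = 1%, there are 0.01 x 900 = 9 cases:

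| t | Number tested | Printed (non-missing) | Over all 900 | Ratio |
|---|---|---|---|---|
| 5% | 45 | 9/45 = 20% | 1% | 20 |
| 10% | 90 | 9/90 = 10% | 1% | 10 |
| 20% | 180 | 9/180 = 5% | 1% | 5 |
| 30% | 270 | 9/270 = 3.3% | 1% | 3.3 |
| 50% | 450 | 9/450 = 2% | 1% | 2 |

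Across the full assumed ranges, the printed figure runs from 0.5%/50% = 1% to 2%/5% = 40%. The inflation is present for any t below 100%.

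**Step 2. Effect on the comparison.** Take c = 1% in both arms, with t = 10% on lixivaptan and 20% on placebo. The printed percentages are 1%/10% = 10% and 1%/20% = 5%. Reversing the trigger rates reverses the result. Over everyone sampled, both arms show 1%.

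**Step 3. Missed neutrophil cases.** Let s be the share of true cases that come with an abnormal total white count. Then c = true rate x s. With a true rate of 2% and s = 50%, c = 1%. At t = 20% the default prints 5%, and the all-sampled denominator prints 1%. Neither is 2%, so changing the denominator replaces an overstatement with an understatement. As an example of a missed case, a white count of 4.5 with 30% neutrophils gives 4.5 x 0.30 = 1.35. If the laboratory's normal range includes 4.5, no differential is reported.

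**Step 4. Shift and change tables.** SAP 9.3 takes as baseline the last value before first study drug. Placebo run-in capsules are dispensed at Visit 2, and the only haematology scheduled before that is at Visit 1a (Protocol Table 3). If 5% of participants had an abnormal white count then (assumed), at most 0.05 x 900 = 45 lixivaptan participants could have a baseline neutrophil value. Fewer would also have a later one. The general baseline rule in SAP 6.1.1, the last value before first lixivaptan, adds Visit 3 but keeps the same condition.

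**The case against.** The strongest reply is that the denominator is a default rather than a stated choice. SAP Section 12 says that its rule holds in general and unless otherwise specified. The table shells, where row denominators are often fixed, are a separate document that was not available. An untriggered test could also be regarded as not applicable rather than missing. This limits the certainty, but nothing in the SAP text overrides the default or defines untriggered tests, so the rule as written gives the conditional rate.

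A second reply is that other outputs cover much of the same ground. Total leukocytes have their own unconditional PCS row. The dipstick items have shift tables by arm, clinically significant findings become adverse events, and flagged values appear in listings. All of this stands and lowers the importance, but none of it corrects the PCS percentages. The key safety endpoint, ALT above 3 x ULN, is untouched.

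Some stronger readings are tempting, but the documents do not support them:
- A reader might infer that lixivaptan, by diluting urine, shifts dipstick triggering and biases the arms in a known direction. The documents say nothing about dipstick trigger rates. One of the two scheduled post-randomization urinalyses, Visit 25, falls about 28 days after the last dose.
- A reader might infer that urine leukocytes are affected too. That row has no unit, and leukocytes are also a routine urinalysis item in Table 8, so it may or may not be a microscopy count.
- A reader might infer that the percentages describe participants whose neutrophils were already abnormal. The condition is on the trigger, and a high total white count also triggers the differential.
- A reader might infer that neutropenia with a normal white count can never be found. Protocol Section 7.3 allows additional assessments at the investigator's discretion, so the gap is in scheduled testing.

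**Conclusion.** The point holds for neutrophils and for urine red cells per high-power field. As written, the plan would report their PCS percentages among reflex-tested participants, too high by 1/(share tested) as a rate over everyone sampled, and sensitive to any difference in trigger rates between arms. The direction of the inflation follows from the documents. Its size does not: every rate in the working is an assumption, and no particular inflated percentage should be quoted as expected. For urine leukocytes the question is open.

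The limits on neutrophil capture and on the differential shift and change tables follow directly from Table 8. How few participants those tables would cover again depends on an unstated trigger rate.

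This is a defect of the plan and not of a result. A reader might infer that misleading rates will appear in the study report. SAP Section 12 records that only 5 participants were randomized, that all terminated early in Part 1, and that no statistical analyses will be performed, with only a limited set of summary tables and listings. The practical effect on this trial is therefore small.

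**What to change.** Amend SAP Section 9.3 and carry the change into the table shells, for both parts of the study.

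- **Urine red cells per high-power field:** use as denominator all participants with at least one post-baseline urinalysis. Count an untriggered microscopy as criterion not met, and show the number reflex-tested beside the percentage.
- **Neutrophils:** choose one of two options. Either remove the PCS percentage and the differential shift and change tables, and list the differential among samples with an abnormal white count. Or show the count over all participants with a post-baseline white count, labelled as reflex-detected, with the number tested.
- **Urine leukocytes:** state the unit and whether the row refers to dipstick or microscopy. If microscopy, treat it as for red cells.

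These changes cost a few sentences of SAP wording and some table footnotes. Reporting the differential on every sample would close the neutrophil gap fully, but it is optional and not a wording change: it alters Protocol Table 8, so it needs an amendment and a change at the central laboratory. The documents do not say whether the laboratory already generates an unreported differential.
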